6.11. Data management

Data will be collected from the two registrations in a dedicated e-CRF in the DANBIO database.

Access to DANBIO is restricted by username and password and access to the study related data is

restricted to research personnel. DANBIO use data logging to create an audit trail thereby registering

e.g., who gains access to, is changing or entering data. In the e-CRF the following data will be entered

by the patient: VAS pain, VAS fatigue, VAS global assessment, PASS and anchoring question and

for patients with axial involvement BASDAI and BASMI as described in section 6.7. Outcomes. For

demographic description of the participants included in this study, the following information is col-

lected from the DANBIO database: gender, age, diagnosis, disease duration, serological status, x-ray

status, last CRP value, last joint assessment, last VAS physician, treatment with NSAID, DMARD,

biologics or prednisolone and for patients with SpA last BASMI score.

In this study, data quality will be promoted through required data entry after each question. All study-

related data will be destroyed 15 years after the end of this study.

7. ETHICS

7.1. Ethical consideration

This study will be conducted in compliance with the protocol, Good Clinical Practice (GCP) and the

Helsinki Declaration. The local Ethics Committee has categorised this study as a register study/ques-

tionnaire study and thus the study does not need to be approved by the Ethics Committee. As de-

scribed in section 7.3. Informed consent, the written informed consent is obtained from the partici-

pants by mail. The data collection of PROM in the rheumatology outpatient clinic at Aalborg Uni-

versity Hospital can be scheduled after the patient's wishes e.g. in connection to scheduled blood

sampling, thus the time consumption in this study is considered acceptable. This study has no influ-

ence on the patient's current or future treatment. The participant will be informed about random find-

ings of clinical significance if permission is given on the informed consent form.

Side **14** af **27**

The study is expected to contribute with information about electronic data collection of PROM through a smartphone app compared to the traditional touch screen solution in the rheumatology out-

patient clinic. In light of the above, it is considered ethically justifiable to conduct the study.

7.2 Recruitment procedures

All patients with RA, PsA or SpA from the rheumatology outpatient clinic at Aalborg University hospital are requested for a telephone contact if the patient is interested in learning more about participation in this study. The request will state, that the telephone contact will be regarding participation in a small research project examine data entry through the touch screen solution versus a smartphone app. The request is made through the touch screen solution in the outpatient clinic in connection to a visit after the patients has registered their PROM data as usual. The patient must enter his/her mobile number for contact if he/she is interested in participation in the study.

7.3. Informed consent

Participants are recruited through the DANBIO touch screen solution in the outpatient clinic as described in section 7.2 Recruitment procedures. LU will receive a list from Zitelab with telephone numbers on patients interested in participation in this study. The possible participants are contacted by telephone and informed about the study by LU. If the participant provides oral consent to receive further information about the study, the participant information is send to the patient by his/her email. The participant's email address is provided by the patient during the telephone call, where the patient also verify access to a smartphone that can download and run the DANBIO app. If the patient wishes to participate in the study, he/she is asked to sign the informed consent form and email it to LU or to give it to research personnel at the rheumatology outpatient clinic. Thereafter, LU will screen the possible participant for the inclusion criteria and exclusion criteria through DANBIO. If the possible participant fulfil the eligibility criteria, LU sign and date the informed consent form and the patient is included in the study. The participant is then randomised to group AT or group TA. For practical reasons, the participant must agree to enter data in both solutions within 1-2 weeks after the informed consent has been signed – however, there must be a "washout period" of 1 day between the two registrations.

8. APPROVAL

This study must be approved by the Danish Data protection Agency before enrolment of participants. This calibration project/agreement study is part of the ELECTOR EU project exploitation plan, thus the ELECTOR steering committee is informed about the conduct of this study and has approved it. This study is part of the Horizon 2020 ELECTOR project.

Zitelab ApS is partner in the ELECTOR consortium

9. CONFIDENTIALITY

In this study, PROM information will be passed on from the participant through a touch screen solution in the outpatient clinic and through the DANBIO app on a smartphone. The information is stored in the DANBIO database in the e-CRF. This information is used to evaluate if electronic data registration through the DANBIO app is comparable with the touch screen solution in the outpatient clinic. All study-related information will be stored securely at the study sites or in the e-CRF in DANBIO. All study-related data in the e-CRF will be identified by a coded ID number to maintain participant confidentiality, however, this does not apply for records that contain names or other personal identifiers, such as informed consent forms, which will be stored with the TMF in locked file cabinets in areas with limited access, thus away from study records identified by ID number. The code for the ID numbers is stored safely in another locked file cabinet in areas with limited access away from all other study-related data. Access to the e-CRF in DANBIO will be excluded to LU. The DANBIO database meets current data security requirements because of data logging, which create an audit trail as explained in section 6.11. Data management. All study-related data will not be made available to a third party with the exception of authorized representatives of the relevant health or regulatory authorities, e.g. the Ethics Committee. This study will comply with The Danish laws regarding patient confidentiality (Lov om behandling af personoplysninger og Sundhedsloven) and is reported to the Danish Data Protection Agency. Data will be destroyed 15 years after the end of this study.

10. COMPENSATION

Study participants will not be financially reimbursed in this study. Research personnel including investigators will not be financially reimbursed for enrolling participants in this study.

11. DISSEMINATION POLICY

This study will be registered on Clinicaltrials.gov before enrolling patients.

All results of this study will be published e.g., in English-language peer reviewed medical journals

as well as presented at international congresses. Both negative, inconclusive and positive research

results will be reported. [name] will be first author, [name], [name],

[name] and [name] will be co-authors and [name] will be last

author. Other authors will be dependent on the contributions. The Vancouver rules for authorship will

be followed.

12. BUDGET

This study is performed without any funding; however, LU's salary is funded by the Rheumatology

Department at Aalborg University Hospital, where LU is employed. The DANBIO app is developed

and owned by Zitelap.

13. TIME SCHEDULE

Recruitment of participants will start after relevant authorities approve this protocol and is scheduled

to start January 2018 and last until the target population is achieved (presumably no longer than 3

months).

Appendix 1: VAS pain, fatigue and global health

Below is the Danish version of the Patient VAS-questionnaires used DANBIO. The left of the VAS scale (0 mm) signifies the absence of symptoms and the right end (100 mm) maximum activity in terms of the parameters assessed.

Question 1 regards the patient's assessment of pain within the last week on a 100 mm horizontal VAS scale (VAS Pain)

Question 2 regards the patient's assessment of fatigue within the last week on a 100 mm horizontal VAS scale (VAS Fatigue)

Question 2 regards the patient's global assessment of disease activity (arthritis severity) within the last week on a 100 mm horizontal VAS scale (VAS Global Health)

De bedes besvare de følgende tre spørgsmål ved at sætte en kort streg gennem linien på det punkt, som De mener passer til svaret på spørgsmålet.

Forkert	Rigtigt •	
X X -		
1. Hvor mange gigtsmerter har De for tiden?		
Ingen gigtsmerter	Uudholdelige gigtsmerter	
2. Hvor træt er De for tiden?		
Slet ikke	Uudholdeligt meget	
3. Hvor meget påvirker gigten som helhed Dere	es tilværelse for tiden?	
Slet ikke ——————————————————————————————————	Uudholdeligt meget	

Clinical Trials number: NCT03486613

Appendix 2: HAQ

HAQ assess the patient's physical function and consist of 20 questions regarding eight different aspects of functional activities. Is answered by the patient on a scale from zero (no disability) to three (completely disabled).

Below is a copy of the Danish version of the HAQ used in DANBIO and in this study:

Clinical Trials number: NCT03486613

Husk kun at sætte ét kryds ved hvert spørgsmål. Hvis De bruger hjælpemidler, skal De svare på, hvordan De klarer Dem med hjælpemidler. Ja, med noget besvær Ja, med meget besvæ Nej, det kan jeg ikke Ja, uden Kan De selv klæde Dem på? (det gælder også snørebånd og knapper) Kan De selv vaske Deres hår? Kan De rejse Dem fra en spisestuestol? Kan De selv klare at komme i og ud af en seng? Kan De selv skære et stykke stegt kød i stykker? Kan De løfte en fyldt kop eller et fyldt glas? Kan De selv åbne en ny mælkekarton? Kan De selv gå rundt udendørs, hvor der er fladt? Kan De selv gå 5 trin op ad en trappe? Ja, uden Ja, med Ja, med Nej, det kan jeg ikke noget besvær meget besvær Kan De selv vaske og tørre Dem over det hele? Kan De selv tage karbad? Kan De selv klare toiletbesøg? Kan De nå op, og hente noget tungt ned fra en hylde over hovedhøjde (f.eks. 2 kg sukker)? Kan De selv samle f.eks. tøj op fra gulvet? Kan De selv åbne en bildør? Kan De skrue låget af et glas, der har været åbnet før? Kan De åbne og lukke en almindelig vandhane? Kan De selv klare indkøb og andre ærinder? Kan De selv komme ind og ud af en bil? Kan De selv klare husarbejdet f.eks. støvsugning eller lettere havearbejde? 3

Appendix 3: PASS

[figure not shown]
PASS is used to access the patient's acceptable symptom state and consist of one question answered with "yes" or "no. In DANBIO the Danish PASS question states:

Clinical Trials number: NCT03486613

"Tænk på alle de måder, som din gigt har påvirket dig de seneste 48 timer. Hvis du i de kommende måneder fortsatte med at have det, som du har haft det de seneste 48 timer, ville det så være acceptabelt for dig?"

Appendix 4: Anchoring question

The anchoring question is used to access if the patient's arthritis has changed since the last visit and is answered with "much worse", "worse", "a little worse", "unchanged", "a little better", "better" and "much better". In DANBIO the Danish anchoring question states:

"Siden dit sidste besøg er din gigt blevet:"

Appendix 5: BASDAI

BASDAI is used for patients with axial arthritis. The questionnaire consist of six questions regarding essential symptoms in axial arthritis on a 100 mm horizontal VAS scale

Clinical Trials number: NCT03486613

Sygdomsaktivitet ved morbus Bechterew (MB)

(The Bath Ankylosing Spondylitis Disease Activity Index = BASDAI)

	Angiv sværhedsgraden af din træthed.	
	INGEN	MEGET SVÆR
2)	Angiv sværhedsgraden af Bechterew smerter i nakke, ryg, lænd eller hofter,	
	INGEN	MEGET SVÆR
3)	Angiv sværhedsgraden af smerter i andre led end nakke, ryg, lænd eller ho	ofter.
	INGEN	MEGET SVÆR
4)	Angiv sværhedsgraden af ubehag i områder, som er ømme ved tryk eller b	erøring.
	INGEN	MEGET SVÆR
5)	Angiv sværhedsgraden af din morgenstivhed.	
	INGEN	MEGET SVÆR
	Angiv tiden indtil din morgenstivhed begynder at aftage.	
()		

Appendix 6: BASFI

BASFI is used for patients with axial arthritis. The questionnaire consist of ten questions regarding physical function on a 100 mm horizontal VAS scale.

Clinical Trials number: NCT03486613

Funktionsindeks ved morbus Bechterew

(The Bath Ankylosing Spondylitis Function Index = BASFI)

1)	Kan du tage strømper på uden hjælp eller brug af hjælpemiddel (f.eks. et s	trømpehjælpemiddel)?
	LET	UMULIGT
2)	Kan du uden brug af hjælpemiddel bøje fremover i ryggen (evt. med let bø en kuglepen op fra gulvet?	iede knæ) og samle
	LET	UMULIGT
3)	Kan du række op på en hylde over hovedhøjde uden hjælp eller brug af	hjælpemiddel?
	LET	UMULIGT
4)	Kan du rejse dig fra en spisestuestol uden armlæn uden at bruge hænde form for hjælp?	erne eller anden
	LET	UMULIGT
5)	Kan du uden hjælp komme op fra gulvet, når du ligger på ryggen?	
	LET	UMULIGT
6)	Kan du uden ubehag stå i 10 minutter uden støtte?	
	LET	UMULIGT
7)	Kan du med en fod på hvert trin gå 12-15 trin på en trappe uden at brug anden hjælp?	e gelænderet eller
	LET	UMULIGT
8)	Kan du se dig over skulderen uden at dreje kroppen?	
	LET	UMULIGT
9)	Kan du udføre fysisk krævende opgaver (f.eks. Bechterew øvelser, havea	rbejde eller sport)?
	LET	UMULIGT
0)	Kan du gennemføre en 71/2 timers arbejdsdag (hjemme eller på arbejde)?	
	LET	UMULIGT

Appendix 7: DAS28crp

DAS28crp are a composite score based on 28 joint count for tenderness and swelling, patient VAS global health and CRP level. The DAS28crp formula are:

Clinical Trials number: NCT03486613

 $DAS28crp = 0.56\sqrt{(TJC28) + 0.28\sqrt{(SJC28) + 0.36ln(CRP + 1) + 0.014(GH) + 0.96}}$

TJC28: 28 joint count for tenderness SJC28: 28 joint count for swelling CRP: C-reactive protein in mg/L

GH: patient global assessment of disease activity from 0-10 on the 100 mm VAS scale

The scoring range for DAS28crp are:

High disease activity: DAS28crp ≥ 5.1

Moderate disease activity: DAS28crp = 3.2-5.1

Low disease activity: DAS28crp = 2.6-3.1

Remission: DAS28crp < 2.6

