6.7. Outcomes

In this study, the PROMs listed in table 1 will be collected for the different disease groups (RA, PsA

and SpA). The Minimal Important Difference (MID)/Minimal Clinically Important Difference

(MCID) for the different measures are consistent with data presented previously (3,6–9).

This study will also estimate Disease Activity Score28crp (DAS28crp) using a fixed level for C-

reactive protein (CRP) level of 6, swollen joint count of 0.5 and tender joint count of 1 and Ankylos-

ing Spondylitis Disease Activity Score (ASDAS) using a fixed level for CRP of 6. These data are

based on DANBIO registrations of patients with RA, PsA or SpA from the rheumatology outpatient

clinic at Aalborg University Hospital. In this study, DAS28crp and ASDAS are estimated from the

PROM data to give the clinician an overview of PROM correlating to e.g. remission or high disease

activity.

Side 9 af 27

Clinical Trials number: NCT03486613

Table 1: overview of patient-reported outcome measures in this study

Variable	Disease area	Unit (range)	Aims to assess	MID/MCID	Equivalence margin
HAQ	RA/PsA/SpA	Points (0-3)	Physical function	0.22 points	± 0.11 points
VAS pain	RA/PsA/SpA	mm (0-100)	Pain intensity	10 mm	± 5 mm
VAS fatigue	RA/PsA/SpA	mm (0-100)	Fatigue severity	10 mm	± 5 mm
VAS global health	RA/PsA/SpA	mm (0-100)	Impact on global health	10 mm	± 5 mm
BASDAI	SpA	Points ¹ (0-100)	Disease activity	10 points	± 5 points
BASFI	SpA	Points ¹ (0-100)	Physical function	10 points	± 5 points
PASS	RA/PsA/SpA	Yes/No	Acceptable symptom state	N.A. ²	± 15% points
Anchoring question	RA/PsA/SpA	Transition scale	Change in arthritis activity	N.A. ²	± 1 unit AND
		(much worse [-3]-much better [+3])			± 15% points better
DAS28crp ^{3,4}	RA/PsA	Points (0.96-9.4)	Disease activity	1.2 points	± 0.6 points
ASDAS ³	PsA ¹ /SpA	Points $(0.6-\infty^5)$	Disease activity	1.1 points	± 0.6 points

^{1:} as used in the DANBIO registry

²: not applicable

³: will be estimated using a fixed level for CRP of 6

^{4:} will be estimated using a fixed level for tender and swollen joint count respectively 1 tender joint and 0.5 swollen joint

⁵: no upper limit for ASDAS

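### Appendix 7 puts patient global on 0-10 in DAS28crp although it is collected on 0-100 mm; with the inputs fixed in 6.7, high activity is out of reach on either scale

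*Protocol*

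**What the plan says.** Appendix 7 of the protocol gives the DAS28crp formula, whose last terms are "0.36ln(CRP + 1) + 0.014(GH) + 0.96", and defines its patient-reported input as "GH: patient global assessment of disease activity from 0-10 on the 100 mm VAS scale". The same appendix lists the activity bands, including "Remission: DAS28crp < 2.6", moderate activity from 3.2, and high activity from 5.1.

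The same item is collected on a different scale. Table 1 lists VAS global health in mm from 0 to 100, and Appendix 1 describes the line as running from 0 mm to the "right end (100 mm) maximum activity in terms of the parameters assessed".

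The other inputs are not measured. Section 6.7 sets a "reactive protein (CRP) level of 6, swollen joint count of 0.5 and tender joint count of 1", and footnote 4 to Table 1 repeats that the score "will be estimated using a fixed level for tender and swollen joint count respectively 1 tender joint and 0.5 swollen joint". Section 6.7 also gives the reason for estimating DAS28crp and ASDAS: they are derived from "PROM data to give the clinician an overview of PROM correlating to e.g. remission or high disease" activity. Table 1 gives DAS28crp (RA and PsA) its own equivalence margin of ±0.6 points and a range of 0.96-9.4.

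**The concern.** There are two linked problems. First, a coefficient of 0.014 is applied to an input that Appendix 7 puts on 0-10 and the rest of the protocol puts on 0-100, so the contribution of patient global differs tenfold depending on which place a programmer follows. Second, patient global is the only term left free to vary. The fixed inputs therefore decide which activity bands can occur at all, and one of the two bands named as examples in 6.7 may not be among them.

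At stake is a derived outcome in Table 1 with its own margin. If its scale is wrong, the equivalence statement for DAS28crp is guaranteed in advance. If its range is not stated, a clinician could take the absence of high-activity scores as a finding about the patients.

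**Working it through.** **Inputs.** Formula, GH definition and cut-offs: Appendix 7. Fixed values TJC 1, SJC 0.5, CRP 6: section 6.7 and footnotes 3 and 4 of Table 1. Collected scale 0-100 mm: Table 1 and Appendix 1. Margin ±0.6: Table 1. Each square root is taken to cover only its own joint count. Read as nested roots, as the formula appears in the text, the fixed inputs would give about 0.67-0.69, below Table 1's stated minimum of 0.96, so that layout is treated as a text-extraction artefact.

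**The plan's own range first.**
- With all inputs at zero the formula gives 0.96, which matches Table 1.
- With 28 tender and 28 swollen joints, it gives 6.80 + 0.36 ln(CRP+1) at GH = 100 and 5.54 + 0.36 ln(CRP+1) at GH = 10.
- No maximum CRP is stated, so the upper figure of 9.4 cannot be confirmed. It would need a CRP of about 1,350 mg/L at GH = 100 and about 44,700 mg/L at GH = 10. The stated range therefore fits 0-100 far better than 0-10.

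**Fixed part of the score.**
0.56 x √1 + 0.28 x √0.5 + 0.36 x ln 7 + 0.96 = 0.560 + 0.198 + 0.701 + 0.960 = 2.419.
Hence DAS28crp = 2.419 + 0.014 x GH.

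**GH on 0-10, as Appendix 7 says.**
- Range: 2.419 to 2.419 + 0.14, that is 2.42 to 2.56. All values are below 2.6.
- Largest possible app-touch difference in one patient: 0.014 x 10 = 0.14, so a mean difference cannot exceed 0.14 either.
- The confidence interval cannot reach the margin. Take 20 complete pairs, one disease group. The SD of differences that all lie within ±0.14 is at most 0.14 x √(20/19) = 0.144. The standard error is then at most 0.144/√20 = 0.032, and the 95% half-width at most about 2.1 x 0.032 = 0.07. Even the crude sum 0.14 + 0.07 = 0.21 is well inside 0.6.

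**GH on 0-100 mm, as Table 1 and Appendix 1 say.**
- Range: 2.419 to 2.419 + 1.40, that is 2.42 to 3.82.
- Remission: GH below (2.6 - 2.4185)/0.014 = 13.0 mm.
- Start of moderate activity: (3.2 - 2.4185)/0.014 = 55.8 mm.
- High activity: (5.1 - 2.4185)/0.014 = 191.5 mm, which does not exist on a 100 mm line.
- For scale, the ±0.6 margin corresponds to a mean GH difference of 0.6/0.014 = 42.9 mm. The ±5 mm margin for VAS global health itself is worth 0.07 DAS28crp points.

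**ASDAS, for comparison.** Appendix 8 gives its patient items as 0-10. With CRP 6 the constant is 0.58 x ln 7 = 1.13, and the four items add at most (0.12 + 0.06 + 0.11 + 0.07) x 10 = 3.60. The range 1.13 to 4.73 reaches all four Appendix 8 bands, from remission (below 1.3) to very high (above 3.5).

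**The case against.** The best case for the plan is this. The 0-10 is very probably a slip: the line that contains it also names a 100 mm scale, and Table 1, Appendix 1 and the stated 0.96-9.4 range all point to 0-100. The fixed values are disclosed and deliberate, since 6.7 says they come from registrations at this clinic, and in a within-patient comparison identical constants cancel. Agreement is judged on the continuous difference, not on activity bands. DAS28crp is neither the primary outcome nor named in the list in 6.7.2. The purpose sentence in 6.7 covers two scores, and ASDAS can meet it.

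Most of this stands and limits the point. Three stronger readings are tempting, and the documents do not support them:

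- A reader might infer that the trial will report every RA and PsA patient as being in remission. The protocol specifies no analysis by activity category. The result would also require the collected millimetres to be rescaled to 0-10 with the 0.014 coefficient kept.
- A reader might infer that, even on 0-100, the bands say more about the constants than about the patient. On that scale GH alone moves a patient through three bands.
- A reader might infer that the fixed inputs are an error and must be replaced. Section 6.7 presents the score openly as an estimate from fixed inputs, so scores that differ from patients' actual disease activity contradict nothing.

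Two things remain. The slip is not harmless, because Appendix 8 states the same patient-global item as 0-10 for ASDAS, and a programmer could rescale it for both scores and follow Appendix 7 to the letter. And correcting the scale does not bring high activity within reach.

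**Conclusion.** The point holds as a scale contradiction together with a stated purpose that DAS28crp cannot fully serve. On the scale printed in Appendix 7, the score can vary by only 0.14 points, never leaves the remission band, and cannot fail its ±0.6 margin. On the scale used for data collection, it varies by 1.40 points (2.42 to 3.82) and covers remission, low and moderate activity, but never high. The shortfall comes from combining the Appendix 7 formula with the values fixed in 6.7; the appendix itself fixes no joint count or CRP.

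This rests on each root covering only its own joint count and on the fixed values being used as 6.7 states. It concerns RA and PsA, the groups for which Table 1 lists DAS28crp. ASDAS, HAQ, the primary conclusion and the sample size are unaffected.

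**What to change.** 1. In Appendix 7, define GH in mm from 0 to 100, in line with Table 1 and Appendix 1. Leave the 0-10 items of ASDAS in Appendix 8 as they are, and note that the two formulas take patient global on different scales.
2. In 6.7, for DAS28crp only, remove or limit the statement about high disease activity. One added sentence is enough: with the fixed inputs the score can only lie between 2.42 and 3.82, so high activity cannot be shown. The statement can stay for ASDAS.

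Both are text corrections. They need no new data and leave the VAS global comparison as it is.

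Optionally, the team could use each participant's last recorded CRP and joint counts, identically for both devices. Section 6.11 already extracts them ("status, last CRP value, last joint assessment, last VAS physician, treatment with NSAID, DMARD"), though for demographic description. In complete pairs they cancel, so the device difference would still be 0.014 x the difference in GH. The protocol does not say how old or how complete these values are, and a missing value would cost that patient's score, so this is a choice for the team and not a required correction.
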